### **12.4.5 Sensitivity analyses**

Not applicable.

### **12.4.6 Supplementary analysis**

Similar analyses will be performed by using valid assessments of antibody assay without imputation of missing data.

## **12.5 Analysis supporting secondary objectives**

In addition to assess immune response at other than  $\geq 14$  days after full course, the following variables will also be evaluated.

- Immune conversion is defined as:
  - Baseline absence of SARS-CoV-2 qualitative IgG antibody with post-vaccination SARS-CoV-2 qualitative IgG antibody assay 14 days after full course (two doses) vaccination (yes/no); or
  - Baseline serum presence of SARS-CoV-2 quantitative antibody with post-vaccination  $\geq 4$ -fold increase in SARS-CoV-2 quantitative antibody titer as determined by dilution assay 14 days after full course (two doses) vaccination (yes/no).
  - Initial negative SARS-CoV-2 nucleocapsid antibody with post-vaccination SARS-CoV-2 positive qualitative antibody assay  $\geq 14$  days after vaccination (yes/no) (Applicable to Cohorts 4 and 5.)

Those variables will be summarized by frequency count and percentage together with the 95% confidence intervals for the proportion of responders obtained using exact method.

Both non-responder imputation of missing data and observed case approach (no imputation for missing data) will be used in the above analyses.

Participants may be enrolled after receiving at least 1 or more mRNA booster or may receive a booster during the trial. This group will be segregated for further analysis.

### **12.5.1 Safety endpoints**

All listings and tables will be presented by cohort.

In particular, summary tables for adverse events (AEs) will summarize only on-treatment events, which started or worsened during the on-treatment period (treatment-emergent AEs).

## **Adverse events**

All information obtained on adverse events will be displayed by cohort and participant.

The number (and percentage) of participants with treatment emergent adverse events will be summarized in the following ways:

[figure not shown]
- by cohort, primary system organ class and preferred term.
- by cohort, primary system organ class, preferred term and maximum severity.
- by cohort, preferred term in descending order

Separate summaries will be provided for study medication related adverse events, serious adverse events, and other significant adverse events leading to discontinuation.

In addition, a separate listing of death including on treatment and post treatment deaths will be provided.

### **Clinical laboratory evaluations**

All laboratory data will be listed by cohort, participant, and visit/time and if normal ranges are available abnormalities will be flagged. Summary statistics will be provided by cohort. Shift tables using the low/normal/high/ (low and high) classification will be used to compare baseline to the worst on-treatment value.

### **12.7 Interim analyses**

For the purpose of early dissemination of results, an interim analysis will be performed once Cohorts 2 and 4 in combination have at least 10 patients enrolled that have had their serum drawn  $\geq$  14 days after full vaccination (two dose) course.

A second interim analysis will be performed once Cohort 6 has at least 10 participants.

The third interim analysis will be performed once Cohorts 2-5 have full enrollment with blood drawn  $\geq$  14 days after full course (two doses) vaccination.

The following variables (but not limited to) will be summarized for each interim analysis mentioned above:

- Demographics
- Baseline characteristics
- Immune response related variables
- AE, SAE, AEs leading to study discontinuation and death

Since there will be no hypothesis testing involved, statistical adjustment for the interim analysis will not be made at the stage of final analyses.

## 12.8 Sample size calculation

### 12.8.1 Primary endpoint(s)

The sample size of 20 participants per cohort is selected based on budget and need for early availability of results. This sample size of 20 participants will provide estimates of proportion of responders with margin of error (half-width of a 95% confidence interval) of 20.1%, 19%, and 17.5% corresponding to response rates of 70%, 75%, and 80%, respectively. Adjusting for 10% drop-out, 22 participants will be enrolled in Cohort 1. In combination, 22 participants will be enrolled in Cohorts 2 and 4. In combination, 22 patients will be enrolled in Cohorts 3 and 5. In Cohort 6, 22 participants will be enrolled.

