	
Participants in Cohort 1 (Moderna vaccine): The first of three 20 mg sc ofatumumab loading doses will be administered on Day 43 or 2 weeks after receiving a full course (two doses) of COVID-19 vaccine. The 2nd and 3rd loading doses should be administered on Day 50 and Day 57 or 7 and 14 days respectively after the 1st loading dose. Subsequent dosing includes 20 mg sc administered monthly starting at Day 71.
 
Participants in Cohort 2: Will continue to take prescribed ofatumumab as per their current dosing schedule.
 
Participants in Cohort 3: Will continue to take interferon or glatiramer acetate as per their current dosing schedule.
 
Participants in Cohort 4: Will continue to take prescribed ofatumumab as per their current dosing schedule.
 
Participants in Cohort 5: Will continue to take prescribed glatiramer acetate or interferon as per their current dosing schedule.
 
Participants in Cohort 6: Will continue to take prescribed ofatumumab as per their current dosing schedule.

Treatment of interest	COVID-19 mRNA vaccine
Efficacy assessments	None
Key safety assessments	

• SARS-CoV-2 qualitative/quantitative IgG antibody assay

• Adverse events/serious adverse events

 
Data analysis	
The primary endpoint is achieving immune response as defined by a positive SARS-CoV-2 qualitative IgG antibody assay 14 days after full course (two doses) vaccination (yes/no).
 
The sample size of 20 participants per individual or combined cohort is selected based on budget and need for early availability of results. The sample size of 20 participants will provide estimates with margin of error (half-width of a 95% confidence interval) of 20.1%, 19%, and 17.5% corresponding to immune response rates of 70%, 75%, and 80%, respectively. Adjusting for 10% drop-out, 22 participants will be enrolled in Cohort 1. In combination, 22 participants will be enrolled in Cohorts 2 and 4. In combination, 22 patients will be enrolled in Cohorts 3 and 5. In Cohort 6, 22 participants will be enrolled.
 
The number and percentage of responders will be presented. The 95% confidence interval for the proportion of responders will be calculated by using exact method.

Key words	COVID-19, vaccine, ofatumumab, SARS-CoV2, antibody,  open-label

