### **12.1 Analysis sets**

The Safety Set comprises all participants who signed informed consent and met all entry criteria.

The Safety Set will be used for the summary of demographic and baseline characteristics as well as for all safety analyses.

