## **12.4 Analysis supporting primary objectives**

The primary objective of this study is to characterize those achieving immune response after receiving vaccination of non-live mRNA COVID-19 vaccine (Pfizer or Moderna vaccine) in subjects treated with ofatumumab 20 mg s.c. once monthly. This will be achieved by estimating the immune response rate using the Safety Set.

An immune responder is a participant achieving immune response as defined by a positive SARS-CoV-2 qualitative antibody assay after vaccination.

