### **12.4.2 Statistical model, hypothesis, and method of analysis**

The number and percentage of responders will be presented. The 95% confidence interval for the proportion of responders will be calculated by using exact method.

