### **12.4.3 Handling of intercurrent events of primary estimand**

Non-responder imputation approach will be applied to missing postvaccination antibody assay regardless of intercurrent events.

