2.5.2 Statistical hypothesis, model, and method of analysis

The number and percentage of responders will be presented by cohort group and overall. The 2-sided 95% CI for the proportion of responders will be calculated using an exact method ([Clopper and Pearson, 1934](#)).

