2.13 Interim analysis

For the purpose of early dissemination of results, an IA will be performed once Cohorts 2 and 4 in combination have ≥ 10 participants enrolled that have had their serum drawn ≥ 14 days after full course (2 doses) vaccination.

A second IA will be performed once Cohort 6 has ≥ 10 participants.

The third IA will be performed once Cohorts 2 – 5 have full enrollment with blood drawn ≥ 14 days after full course (2 doses) vaccination.

The following variables (including but not limited to) will be summarized for each IA mentioned above:

- Disposition
- Demographics

- Baseline characteristics
- Immune response-related variables
- AEs, SAEs and AEs leading to study discontinuation
- Deaths

Since there will be no hypothesis testing involved, statistical adjustment for the IA will not be made at the stage of final analyses.

3 Sample size calculation

The sample size of 20 participants per cohort is selected based on budget and need for early availability of results. This sample size of 20 participants will provide estimates of proportion of responders with margin of error (half-width of a 95% CI) of 20.1%, 19% and 17.5% corresponding to response rates of 70%, 75% and 80%, respectively. Adjusting for 10% drop-out, 22 participants will be enrolled in Cohort 1. In combination, 22 participants will be enrolled in Cohorts 2 and 4. In combination, 22 participants will be enrolled in Cohorts 3 and 5. In Cohort 6, 22 participants will be enrolled.

4 Change to protocol specified analyses

There are no changes to protocol specified analyses.

5 Appendix

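### The stated 95% CI margins for 20 participants (20.1, 19 and 17.5 points) come from the normal approximation; the planned exact interval gives 21.2, 20.2 and 19.0 and is asymmetric

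*Protocol*

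**What the plan says.** Protocol 12.8.1 sets 20 participants per cohort on grounds of budget and speed. It then says what precision this will give: a "margin of error (half-width of a 95% confidence interval) of 20.1%, 19%, and 17.5% corresponding to response rates of 70%, 75%, and 80" per cent. The Data analysis entry of the protocol summary has the same figures ("margin of error (half-width of a 95% confidence interval) of 20.1%, 19%, and 17.5% corresponding to immune response rates of 70%, 75%, and 80" per cent), and so does SAP Section 3, Sample size calculation ("margin of error (half-width of a 95% CI) of 20.1%, 19% and 17.5" per cent). Allowing for 10% drop-out, 22 are to be enrolled in each of four groups: Cohort 1, Cohorts 2 and 4, Cohorts 3 and 5, and Cohort 6.

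For the analysis itself, Protocol 12.4.2 says: "The 95% confidence interval for the proportion of responders will be calculated by using exact method". SAP 2.5.2 says the two-sided 95% interval "will be calculated using an exact method" and cites Clopper and Pearson. The protocol summary states the margins and the exact method in the same entry.

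Two further rules set the denominator. Protocol 12.4 says of the primary objective: "This will be achieved by estimating the immune response rate using the Safety Set". Protocol 12.1 defines that set: "The Safety Set comprises all participants who signed informed consent and met all entry criteria". Missing assays count as failures under Protocol 12.4.3: "Non-responder imputation approach will be applied to missing postvaccination antibody assay regardless of intercurrent events".

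**The concern.** The margins are presented as what the sample will deliver, with no method named and no note that they are approximate. The only interval for a proportion named in either document is the exact one. At n = 20 and rates of 70% to 80%, the exact interval is wider than the normal-approximation interval and is not centred on the estimate, so a single symmetric margin does not describe it.

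The sample size rests on no power calculation or precision target, so these three margins are the plan's only quantitative statement of what the sample can show. The primary question is whether ofatumumab-treated participants mount a response. The lower confidence limit is therefore the informative end, and that is the end where the stated margins are too optimistic.

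**Working it through.** **Inputs.** n = 20, 95% confidence, rates of 70%, 75% and 80%, and stated half-widths of 20.1, 19 and 17.5 points (Protocol 12.8.1). Planned method: Clopper-Pearson, two-sided 95% (SAP 2.5.2). Enrolled per group: 22.

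**Step 1: reproduce the stated figures.** Normal-approximation half-width = 1.96 × √(p(1−p)/n).

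- 70%: 1.96 × √(0.70 × 0.30/20) = 20.08 points
- 75%: 1.96 × √(0.75 × 0.25/20) = 18.98 points
- 80%: 1.96 × √(0.80 × 0.20/20) = 17.53 points

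These round to the stated 20.1, 19 and 17.5. None of the other methods tried gives that set:

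- Wilson: 18.7/17.8/16.8
- Agresti-Coull: 18.9/18.2/17.3
- Jeffreys: 19.1/18.1/16.8
- t quantile: 21.4/20.3/18.7
- Normal with continuity correction: 22.6/21.5/20.0

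**Step 2: apply the planned method.** For x responders of n, the lower limit is the 2.5% quantile of Beta(x, n−x+1) and the upper limit is the 97.5% quantile of Beta(x+1, n−x).

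| Responders | Exact 95% CI (%) | Half-width | Below estimate | Above estimate | Half-width minus stated |
|---|---|---|---|---|---|
| 14/20 (70%) | 45.72 to 88.11 | 21.19 | 24.28 | 18.11 | 1.09 |
| 15/20 (75%) | 50.90 to 91.34 | 20.22 | 24.10 | 16.34 | 1.22 |
| 16/20 (80%) | 56.34 to 94.27 | 18.96 | 23.66 | 14.27 | 1.46 |

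The last column is measured against the rounded figures in the documents. Against the unrounded normal values the excess is 1.11, 1.25 and 1.43 points. The full exact interval is 2.2 to 2.9 points wider than the normal one.

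**Step 3: compare limits.** The documents print no limits. The implied limits below are the rate minus and plus the stated margin.

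| Rate | Implied by stated margin (%) | Exact (%) | Exact lower limit is lower by | Exact upper limit is lower by |
|---|---|---|---|---|
| 70% | 49.9 to 90.1 | 45.7 to 88.1 | 4.18 | 1.99 |
| 75% | 56.0 to 94.0 | 50.9 to 91.3 | 5.10 | 2.66 |
| 80% | 62.5 to 97.5 | 56.3 to 94.3 | 6.16 | 3.23 |

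**Step 4: use all 22 enrolled as the denominator.** With non-responder imputation on the Safety Set, drop-outs who met entry criteria remain in the denominator. The three rates then correspond to 15.4, 16.5 and 17.6 responders. These are not whole numbers, so the results are interpolations.

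| Rate | Exact 95% CI, n = 22 (%) | Half-width | Minus stated | Lower limit below implied |
|---|---|---|---|---|
| 70% | 46.97 to 87.41 | 20.22 | 0.12 | 2.93 |
| 75% | 52.18 to 90.76 | 19.29 | 0.29 | 3.82 |
| 80% | 57.65 to 93.80 | 18.07 | 0.57 | 4.85 |

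**The case against.** The stated figures are computed and rounded correctly for the formula that produces them. The documents refer only to a 95% confidence interval and never claim these half-widths are exact. A normal-approximation margin is a common planning shorthand. No precision target is set, no hypothesis is tested, and the reported interval will be the exact one whatever the sample size section says. The primary denominator may also be 22 rather than 20, which cuts the half-width gap to 0.1 to 0.6 points. Finally, precision is not overstated on the upper side: the exact upper arm is shorter than the stated margin at all three rates.

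Much of this stands, and it limits the weight of the point. The fault is a mismatch between the planning formula and the analysis method, not a slip in calculation, and the understatement lies wholly below the estimate. The mismatch itself remains. The text ties its margins to 20 participants, does not call them approximate, and sits beside a plan that names only the exact method. Moving to 22 does not rescue the figures: every exact half-width is still above its stated value, and the lower limits are still about 3 to 5 points below those implied.

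**Conclusion.** The concern holds and is minor. At the stated n of 20, the planned interval has half-widths of 21.2, 20.2 and 19.0 points rather than 20.1, 19 and 17.5. A single margin also hides a lower arm of about 24 points at all three rates.

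That the stated figures are normal-approximation values is inferred from reproducing them, since the documents name no method. The mismatch with the exact interval does not depend on that inference. The n = 20 results assume exactly 14, 15 or 16 responders. The n = 22 results assume that all enrolled participants meet entry criteria and stay in the denominator. Enrolment, analysis and conclusions are unaffected.

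**What to change.** In the protocol summary, Protocol 12.8.1 and SAP Section 3, replace the sentence giving the margins with:

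> With 20 participants, the exact (Clopper-Pearson) 95% CI would be 45.7% to 88.1% for 14/20 (70%), 50.9% to 91.3% for 15/20 (75%) and 56.3% to 94.3% for 16/20 (80%).

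This is a text edit in three places, and the stated precision becomes slightly less favourable. Protocol 14.1 requires a written amendment for the two protocol edits. They can go into the next amendment and need not prompt one. Enrolment and the analysis stay as planned.

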## 13 Ethical considerations and administrative procedures

### 13.1 Regulatory and ethical compliance

This clinical study was designed and shall be implemented, executed and reported in accordance with the ICH Harmonized Tripartite Guidelines for Good Clinical Practice, with applicable local regulations (including European Directive 2001/20/EC, US CFR 21), and with the ethical principles laid down in the Declaration of Helsinki.

### 13.2 Responsibilities of the investigator and IRB

Before initiating a trial, the investigator/institution must obtain approval/favorable opinion from the Institutional Review Board (IRB) for the trial protocol, written informed consent form, consent form updates, participant recruitment procedures (e.g., advertisements) and any other written information to be provided to participants. Prior to study start, the investigator is required to sign a protocol signature page confirming his/her agreement to conduct the study in accordance with these documents and all of the instructions and procedures found in this protocol and to give access to all relevant data and records to Novartis monitors, auditors, Novartis Quality Assurance representatives, designated agents of Novartis, IRBss, and regulatory authorities as required. If an inspection of the clinical site is requested by a regulatory authority, the investigator must inform Novartis immediately that this request has been made.

### 13.3 Publication of study protocol and results

The protocol will be registered in a publicly accessible database such as clinicaltrials.gov and as required in EudraCT. In addition, after study completion (defined as last patient last visit) and finalization of the study report the results of this trial will be submitted for publication and posted in a publicly accessible database of clinical trial results, such as the Novartis clinical trial results website and all required Health Authority websites (e.g. Clinicaltrials.gov, EudraCT etc.) .

For details on the Novartis publication policy including authorship criteria, please refer to the Novartis publication policy training materials that were provided to you at the trial investigator meetings.

### **13.4 Quality Control and Quality Assurance**

Novartis maintains a robust Quality Management System (QMS) that includes all activities involved in quality assurance and quality control, to ensure compliance with written Standard Operating Procedures as well as applicable global/local GCP regulations and ICH Guidelines.

Audits of investigator sites, vendors, and Novartis systems are performed by auditors, independent from those involved in conducting, monitoring or performing quality control of the clinical trial. The clinical audit process uses a knowledge/risk based approach.

Audits are conducted to assess GCP compliance with global and local regulatory requirements, protocols and internal SOPs, and are performed according to written Novartis processes.

## **14 Protocol adherence**

This protocol defines the study objectives, the study procedures and the data to be collected on study participants. Additional assessments required to ensure safety of participants should be administered as deemed necessary on a case by case basis. Under no circumstances including incidental collection is an investigator allowed to collect additional data or conduct any additional procedures for any purpose involving any investigational drugs under the protocol, other than the purpose of the study. If despite this interdiction prohibition, data, information, observation would be incidentally collected, the investigator shall immediately disclose it to Novartis and not use it for any purpose other than the study, except for the appropriate monitoring on study participants.

Investigators ascertain they will apply due diligence to avoid protocol deviations. If an investigator feels a protocol deviation would improve the conduct of the study this must be considered a protocol amendment, and unless such an amendment is agreed upon by Novartis and approved by the IRB and Health Authorities, where required, it cannot be implemented.

### **14.1 Protocol amendments**

Any change or addition to the protocol can only be made in a written protocol amendment that must be approved by Novartis, health authorities where required, and the IRB prior to implementation.

Only amendments that are required for participant safety may be implemented immediately provided the health authorities are subsequently notified by protocol amendment and the reviewing IRB is notified.

Notwithstanding the need for approval of formal protocol amendments, the investigator is expected to take any immediate action required for the safety of any participant included in this study, even if this action represents a deviation from the protocol. In such cases, Novartis should be notified of this action and the IRB at the study site should be informed according to local regulations.

28-Jun-2023	Prior to clinical DB lock	Creation of Amendment 1	
1. Updated to align with protocol version 01 (amended protocol) dated 29-Sep-2021: added 3 new cohorts; increased sample size; included participants who are fully vaccinated; increased number of interim analyses; addressed inconsistencies and made clarifications2. Updated list of abbreviations3. Clarified primary analysis time point for Cohorts 4-6 as Visit 25. Updated definition of immune conversion to account for participants with serum unavailable prior to vaccine but who have not received a booster (Cohorts 4 and 5)6. Indicated that 95% CIs for point estimates of mean or proportion will be provided7. Clarified that summarization of data will be done via cohort groupings: Cohort 1, Cohorts 2 and 4, Cohorts 3 and 5, and Cohort 68. Changed baseline to pre-vaccination and post-baseline to post-vaccination9. Modified definition of safety analysis set to include participants who signed	
1. Section 1 Introduction; Section 1.1 Study design; Section 1.2 Study objectives, endpoints and estimands; Section 1.2.1 Primary estimand(s); Section 2.1.1 General definitions; Section 2.5.1 Primary endpoint(s); Section 2.13 Interim analysis; Section 3 Sample size calculation2. List of abbreviations table3. Section 1.1 Study design5. Section 1.2 Study objectives, endpoints and estimands; Section 2.6.1 Secondary endpoint(s)6. Section 2.1 Data analysis general information7. Section 2.1 Data analysis general information8. Section 1.2 Study objectives, endpoints and estimands; Section 2.1.1 General definitions; Section 2.6.1 Secondary endpoint(s)9. Section 2.2 Analysis sets10. Section 2.3.1 Patient disposition11. Section 2.3.3 MS history

Date	Time point	Reason for update	Outcome for update	Section and title impacted (Current)
			informed consent and met all entry criteria	12. Section 2.3.4 Medical history
			10. Removed disposition event of Safety follow-up	13. Section 2.4.1 Study treatment / compliance
			11. Added section to address summarization of MS history	14. Section 2.4.1.1 Visit windows
			12. Clarified that medical history will be summarized with frequency counts and percentages	15. Section 2.4.2 Prior, concomitant and post therapies
			13. Added variables for time between points of interest; indicated that MS treatment compliance will be listed	16. Section 2.5 Analysis supporting primary objective(s)
			14. Made updates to visit windows based on protocol amendment and review of data	17. Section 2.5.6 Supplementary analyses
			15. Clarified that non-drug therapies/procedures will be coded per MedDRA terminology and summarized by primary SOC and PT; indicated that prior MS DMTs will be summarized by PT	18. Section 2.6.6 Supplementary analyses
			16. Clarified that the primary analysis will be conducted using the safety analysis set	19. Section 2.7.1 Adverse events (AEs)
			17. Added supplemental analysis in which primary analysis is repeated using data from Cohort 6 participants and any participants in Cohorts 1-5 who received a booster during the study	20. Section 2.7.3 Laboratory data
			18. Added supplemental analysis in which analysis of secondary endpoints is repeated using data from Cohort 6 participants and any participants in Cohorts 1-5 who received a booster during the study	21. Section 2.7.4.1 MS relapse
			19. Removed reference to CTC AE grades	
			20. Added descriptive summary of laboratory assessments	24. Section 5.1.2 AE date imputation; Section 5.1.3 Concomitant medication date imputation
				25. Section 5.1.3.3 Other imputations

Date	Time point	Reason for update	Outcome for update	Section and title impacted (Current)
			21. Modified the categories for summary of number of relapses	[REDACTED]
			24. Replaced AE and medication partial date imputation rules with [REDACTED] standard rules	
			25. Added imputation rule for partial relapse start dates	

Table of contents

Table of contents	5
List of abbreviations	7
1 Introduction	8
1.1 Study design	8
1.2 Study objectives, endpoints and estimands	12
1.2.1 Primary estimand(s)	13
1.2.2 Secondary estimand(s)	14
2 Statistical methods	14
2.1 Data analysis general information	14
2.1.1 General definitions	14
2.2 Analysis sets	16
2.2.1 Subgroup of interest	16
2.3 Patient disposition, demographics and other baseline characteristics	16
2.3.1 Patient disposition	16
2.3.2 Demographics and other baseline characteristics	16
2.3.3 MS history	17
2.3.4 Medical history	17
2.4 Treatments (study treatment, rescue medication, concomitant therapies, compliance)	17
2.4.1 Study treatment / compliance	17
2.4.2 Prior, concomitant and post therapies	23
2.5 Analysis supporting primary objective(s)	23
2.5.1 Primary endpoint(s)	24
2.5.2 Statistical hypothesis, model, and method of analysis	24
2.5.3 Handling of intercurrent events	24
2.5.4 Handling of missing values not related to intercurrent event	25
2.5.5 Sensitivity analyses	25
2.5.6 Supplementary analyses	25
2.6 Analysis supporting secondary objectives	25
2.6.1 Secondary endpoint(s)	25
2.6.2 Statistical hypothesis, model, and method of analysis	26
2.6.3 Handling of intercurrent events	26
2.6.4 Handling of missing values not related to intercurrent event	26

2.6.5	Sensitivity analyses.....	26
2.6.6	Supplementary analyses	26
2.7	Safety analyses	26
2.7.1	Adverse events (AEs)	26
2.7.2	Deaths	27
2.7.3	Laboratory data.....	27
2.7.4	Other safety data	27
2.8	Pharmacokinetic endpoints	27
2.9	PD and PK/PD analyses	27
2.10	Patient-reported outcomes.....	27
2.11	Biomarkers	27
		27
2.13	Interim analysis	28
3	Sample size calculation.....	29
4	Change to protocol specified analyses.....	29
5	Appendix	29
5.1	Imputation rules	29
5.1.1	Study drug.....	29
5.1.2	AE date imputation	29
5.1.3	Concomitant medication date imputation.....	30
5.2	AEs coding/grading.....	32
5.3	Laboratory parameters derivations.....	32
5.4	Statistical models	32
5.4.1	Analysis supporting primary objective(s).....	32
5.4.2	Analysis supporting secondary objective(s)	32
5.5	Rule of exclusion criteria of analysis sets	32
6	Reference	32

List of abbreviations

AE	Adverse Event
ATC	Anatomical Therapeutic Chemical
CDBL	Clinical Database Lock
CI	Confidence Interval
COVID-19	Coronavirus 2019
CRO	Contract Research Organization
CSP	Clinical Study Protocol
CSR	Clinical Study Report
EOS	End of Study
HBV	Hepatitis B Virus
IA	Interim Analysis
IgG	Immunoglobulin G
LS	Least Squares
MedDRA	Medical Dictionary for Drug Regulatory Activities
mRNA	Messenger Ribonucleic Acid
MS	Multiple Sclerosis
NRI	Non-Response Imputation
PD	Pharmacodynamic
PK	Pharmacokinetic
PT	Preferred Term
SAE	Serious Adverse Event
SAF	Safety Analysis Set
SAP	Statistical Analysis Plan
SARS-CoV-2	Severe Acute Respiratory Syndrome Coronavirus 2
s.c.	Subcutaneous
SOC	System Organ Class
WHO	World Health Organization

1 Introduction

The purpose of this Statistical Analysis Plan (SAP) is to describe the statistical methods planned in Section 12 of the Clinical Study Protocol (CSP) version 01 (dated 29-Sep-2021) for the clinical trial COMB157GUS16 and any additional analyses, specifications or deviations from this planned protocol before clinical database lock (CDBL).

This SAP will be used to draft the Clinical Study Report (CSR) Section 9.7: Statistical methods.

